9.3.1.4 Response Criteria

Complete Response (CR)

Disappearance of all target and non-target lesions, determined by two separate observations conducted not less than 4 weeks apart. There can be no appearance of new lesions.

Partial Response (PR)

At least a 50% decrease in the size of target lesions, taking as reference to the baseline MRI. There can be no appearance of new lesions.

Progressive Disease (PD)

At least a 50% increase in the sum of the size of target lesions, taking as reference the smallest target size since the treatment started that is confirmed on a 3 month follow up scan as long as the patient is NOT experiencing significant neurological decline (defined as CTCAE grade 3 or higher). Please also refer to Table 7.1. The confirmatory scan requirement will assure that patients are not prematurely assigned to have PD. Also, the appearance of new lesions might be part of an immune response and if the patient is clinically stable, these should be confirmed on a 3 month follow scan to assess for true progressive disease versus pseudo-progression. This will apply to subjects that demonstrate worsening of the MRI within 6 months of start of therapy. Subjects who develop worsening radiographic findings > 6 months from start of immunotherapy are expected to have a low likelihood of ultimately deriving benefit from the therapy and should be considered PD based on imaging if they have a 50% increase in size of the target lesion or if new lesions appear.

Patients who experience significant clinical decline or those who have radiographic progression on the 3 month follow up scan should be classified as progressive disease and the date of progression should be entered as the first MRI that showed progressive disease.

If the follow up 3 month scan shows stabilization or reduction of tumor size in the setting of stable clinical examination and absence of increased steroid use treatment, the patient will be classified as having pseudo-progression and will continue on study therapy.

If feasible, we recommend obtaining tissue if imaging is concerning for progression, as tissue evaluation remains the gold standard to differentiate between pseudoprogression versus true progression. If pathology mainly consists of recurrent tumor, the subject should be considered to have true tumor progression and be taken off study. If the tissue mainly consists of gliosis and inflammation (consistent with treatment effect) the subject should be classified has having pseudo-progression and should remain on study. Subjects that have tissue available will be centrally reviewed at UCSF.

In cases for which it remains difficult to differentiate between progression versus pseudo- progression, the PI must discuss with the study chair the possibility of continuation of therapy. Images will also be

centrally reviewed at UCSF. Continuation of therapy might be considered if the patient derives clinical benefit with acceptable toxicity after a review by the study chair.

Please refer to outline below to assess PD. This is applicable for imaging findings within the first 6 months since start of immunotherapy.

Stable Disease (SD)

Neither sufficient shrinkage to qualify for PR nor sufficient increase to qualify for PD, taking as reference the smallest target size since the treatment started.

Evaluation of Best Overall Response

The best overall response is the best response recorded from the start of the treatment until disease progression/recurrence (taking as reference for progressive disease the smallest measurements recorded since the treatment started). The patient's best response assignment will depend on the achievement of both measurement and confirmation criteria.

Table 7.1 Response Criteria

Biopsy requirements: If the repeat MRI scan is unchanged or worse, and/or the patient's clinical status has not improved despite the maximum allowed steroid dose (refer to Section 5.2.4), a biopsy (or resection, if clinically indicated) should be performed to differentiate between pseudo- and true tumor progression. If for some reason (e.g., patient refusal or medical/surgical contraindication), a biopsy (or resection) cannot be performed, the patient will be taken off study due to presumed tumor progression. When a biopsy or resection is performed, the histopathological specimen will be carefully examined for evidence of: inflammatory/lymphocytic infiltration (pseudo-tumor progression). If inflammatory/ lymphocytic infiltration and/or necrosis comprise the majority of the specimen, patients may remain on study and restart treatment following resolution of toxicity to grade 1 and if steroids were successfully weaned. Such patients MUST be discussed with the study chair and team. Please also refer to Section 5.2.4 under Pseudo-progression.

Duration of Response

Duration of overall response

The duration of overall response is measured from the time measurement criteria are met for CR or PR (whichever is first recorded) until the first date that recurrent or progressive disease is objectively documented (taking as reference for progressive disease the smallest measurements recorded since the treatment started).

The duration of overall CR is measured from the time measurement criteria are first met for CR until the first date that recurrent disease is objectively documented.

Duration of stable disease

Stable disease is measured from the start of the treatment until the criteria for progression are met, taking as reference the smallest measurements recorded since the treatment started.

Progression-Free Survival

Progression-free survival (PFS) is defined as the duration from diagnosis to time of progression.

Overall Survival

Overall survival (OS) is defined as the duration of time of diagnosis to time of death.

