3.2.1 Inclusion Criteria

Stratum A:

 Newly diagnosed children (3-21 years old) with DIPG who are positive for the H3.3K27M mutation (positive testing from a CLIA or equivalent laboratory required) that underwent standard radiation therapy.

Stratum B:

• Newly diagnosed children (3-21 years old) with diagnosis of midline glioma other than DIPG who are positive for the H3.3K27M mutation (positive testing from a CLIA or equivalent laboratory required), including spinal cord gliomas, that underwent standard radiation therapy.

Stratum C:

• Newly diagnosed children 3-21 years of age with diagnosis of DIPG or midline glioma other than DIPG (excluding primary spinal cord gliomas) who are positive for the H3.3K27M mutation (positive testing from a CLIA or equivalent laboratory required), that underwent standard radiation therapy.

The following eligibility criteria apply to strata A, B and C:

- The patient must test positive for HLA-A*02:01 (positive testing from a CLIA or equivalent laboratory required; only the HLA A*02:01 subtype is eligible; other subtypes are excluded)
- The patient must be either off systemic steroids or be on stable dose of dexamethasone or equivalent (max 0.1 mg/kg/day; maximum 4mg/day) at time of enrollment.
- Patients must not have received any prior chemotherapy, immunotherapy or bone marrow transplant for the treatment of their tumor. Prior use of temozolomide during radiation at maximum of the standard pediatric dosing (defined as 90 mg/m² /dose continuously during radiation therapy for 42 days) or dexamethasone is allowed.
- Patients must have undergone radiation therapy and surgery as part of their standard of care.

- Stratum A: Radiation therapy must have started within 4 weeks of diagnosis by imaging or surgery, whichever is later.
- Stratum B: For subjects undergoing surgery for more extensive resection, radiation therapy should be started within 4-6 weeks from surgery.
- Stratum C: Radiation therapy must have started within 4 weeks of diagnosis by imaging or surgery, whichever is later. For subjects undergoing surgery for more extensive resection, radiation therapy should be started within 4-6 weeks from surgery.
- Karnofsky ≥50 for patients ≥16 years of age, and Lansky ≥50 for patients < 16 years of age (See Appendix A). Patients who are unable to walk because of paralysis, but who are up in a wheelchair, will be considered ambulatory for the purpose of assessing the performance score.

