7.2 Off Study Criteria

Subjects will be considered Off Study for the following reasons:

- Subject determined to be ineligible.
- Parent, subject, or guardian withdraws consent for continued participation.
- Subject death while on study.

Subjects who expire without confirmation of disease status will be considered progressive disease at the time of death.

The date and reason for the subject coming off study must be documented in the 'Follow-Up' section of OnCore® as well as the 'PNOC End of Treatment eCRF' in Advarra®. No data will be collected after the "off study" date.

Table 6.1 Schedule of Study Procedures and Assessments (Strata A and B)

Study Day/Visit	Eligibility (-14 days) ¹	Day 1 on Weeks 0, 3, 6, 9, 12, 15, 18, 21, 24 (-3 days)	Day 1 on Weeks 30, 36, 42, 48, 54, 60, 66, 72, 78, 84, 90, 96 (-3 days) ²	End of Treatment Visit (-14 days) ³	30 Day Toxicity Check (+7 days)⁴	Follow- Up⁵
Clinical procedures						
HLA typing	X6					
H3.3K27M mutation status	X6					
Consent Form	X1					
Physical Exam ⁷		х	х	Х		
Vital Signs		х	х	Х		
Medical History ⁸	Х					
Performance Status	х	х	х	х		
Adverse Event assessment		X٩	Х	х	х	х
Concomitant Medications	х	Х	Х	Х	х	
Vaccination ¹⁰ Vaccine Poly-ICLC¹¹ 		Х				
Evaluation of clinical response				х		
Survival⁵						x
Laboratory procedures						
CBC w/ Diff + plts	х	X ¹²	X ¹²	X ¹²		
Blood Chemistry	X ¹³	X ^{12,13}	X ^{12,13}	X ^{12,13}		
Pregnancy test ¹⁴	х	х	Х	х		
Imaging procedures						
Brain MRI/Spine MRI	X ¹⁵	X ¹⁵	X ¹⁵	X ^{4,15}		
Specimen Collection						
Immune monitoring tests ¹⁶		х	Х			
Blood for ctDNA 17		x	Х			
Tumor Tissue Collection ¹⁸			Х			

- 1. Eligibility tests and procedures must be performed within 14 days prior to enrollment. Consent to study therapy must be signed.
- If the subject demonstrates no evidence of disease progression and tolerates the therapy well (defined as not having any regimen related toxicities (RLT); see Section 6.3) after the 8th dose (Week 21), patients may receive additional vaccinations starting at Week 30, every 6 weeks, for a total of 96 weeks (approximately 2 years).
- 3. End of treatment procedures to occur on last day of treatment. These do not need to be repeated if occurred within 14 days prior. Brain/Spine MRI to be repeated if not done within 30 days prior to the end of treatment visit.
- 4. 30-day toxicity check may be done via telephone if needed (+7 days). Related AEs must continue to be followed until resolution or return to baseline

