- 5. Subjects in the follow up phase will be followed by chart review and/or telephone contact until an off- study criterion is met to collect survival information every three months for 24 months.
- Subjects must be positive for HLA-A2 and H3.3K27M. HLA A*02:01 typing (based on sequencing) and H3.3K27M mutation status must be done in a CLIA- or equivalent approved laboratory. If H3.3K27M mutation analysis is to be performed at UCSF, pathology and imaging (MRI), and tissue must be submitted.
- 7. To include neurological exam.
- 8. To include history of prior treatments and any residual toxicity relating to prior radiation therapy and baseline conditions assessment.
- 9. Adverse assessments to be assessed at all visits following Week 0 vaccine administration.
- 10. All patients will be closely observed for adverse events for at least 20 minutes following each vaccination. Vaccine will not be administered on Week 24 or Week 27. Vaccination will resume on Week 30 and every 6 weeks thereafter, for a total of 96 weeks (approximately 2 years).
- 11. If there is evidence of pseudo-progression after radiation therapy on baseline MRI, poly-ICLC can be held for up to 12 weeks.
- 12. Laboratory assessments do not need to be repeated if completed within 7 days prior.
- 13. Blood chemistry to include: At screening: aspartate aminotransferase/alanine aminotransferase (ALT/AST), total bilirubin, creatinine and albumin. Week 0 and beyond: alkaline phosphatase, aspartate aminotransferase/alanine aminotransferase (ALT/AST), total bilirubin, calcium, phosphorus, blood urea nitrogen (BUN), creatinine, total protein, albumin, glucose, potassium, sodium, chloride, bicarbonate.
- 14. May be serum or urine pregnancy test; for females of child-bearing potential.
- 15. Spinal MRI only required if clinically indicated. Post radiation therapy MRI must occur within 14 days of enrollment and within 14 days of treatment start date (Day 1 Week 0). MRI(s) to be obtained at baseline and then every 12 weeks thereafter (-14 days) at Weeks 12, 24, 36, 48, etc.
- 16. To be obtained at weeks 0 (prior to vaccine), 12, 18, and 24 and then every 12 weeks thereafter each time a MRI is performed (-7 days) (i.e. Week 36, 48, 60, etc.). See Section 9 for further details.
- 17. To be obtained at baseline (Week 0 Day 1) and then every 12 weeks (-7 days).

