If enrollment commences, all additional patients will be monitored continuously for treatment-related adverse events by the study PIs Drs. [name] and [name]. With six patients, there is an 88% probability of detecting 1 or more RLTs with an underlying rate of 30%. There is a 74% probability of detecting 1 or more RLTs with an underlying rate of 20%. If all 19 patients are enrolled in Stratum A, there is an 86% probability of detecting 1 or more RLTs with an underlying rate of 10% and a 62% probability with an underlying rate of 5%. If all 10 patients are enrolled in Strata B, there is a 65% probability of detecting 1 or more RLTs with an underlying rate of 10% and a 40% probability with an underlying rate of 5%. If all 20 patients are enrolled in Strata C, there is an 88% probability of detecting 1 or more RLTs with an underlying rate of 10% and a 64% probability with an underlying rate of 5%.

Enrollment into Stratum C will start once Strata A and B have completed accrual.

- **10.2** Determination of Sample Size and Accrual Rate
- **10.2.1** Sample Size and Power Estimate

For the primary endpoint for stratum A, we will assess the efficacy endpoint (OS12) in 19 evaluable patients with H3.3K27M positive DIPG. Prior research has shown overall survival for children with DIPG ranges from 30-40% at 12 months^{38,39}. The most recent Children's Oncology Group study that treated children newly diagnosed with DIPG with a combination of radiation therapy and temozolomide resulted

in an OS12 rate of 40% (SD \pm 6.5%)¹. Review of outcomes of DIPG patients on PNOC studies of children and young adults with newly diagnosed DIPG who received standard of care radiation therapy revealed an OS12 rate of 50% (PNOC003 - NCT02274987 and PNOC007 - NCT02960230, unpublished data). For PNOC003 patients were enrolled prior to the start of radiation therapy - similar to the COG study- and none of the enrolled patients came off study due to progression during or at completion of radiation therapy making this a reasonable control group for this study.

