10.3.2 Analysis of Primary Endpoints

- Safety of K27M/TT vaccine and poly-ICLC in combination with nivolumab (stratum C only) will be assessed by monitoring for adverse events, scheduled laboratory assessments, vital sign measurements, and physical examinations for subjects who receive at least one course of the study therapy. The severity of toxicities will be graded according to the NCI CTCAE v5.0. Adverse events and will be summarized by maximum intensity and relationship to study drug(s).
- Safety will be assessed every 3 weeks for the first 24 weeks and then every 6 weeks. Descriptive statistics will be utilized to display the data on toxicity seen.
- OS12 in HLA-A02:01⁺ children with H3.3K27M positive DIPG (Stratum A) will be the clinical efficacy primary endpoint. Any subject enrolled (ITT) will be considered evaluable for clinical efficacy. Patients lost to follow-up before 12 months will be considered events and the OS probability at 12 months (OS12) will be estimated from the Kaplan-Meier method. Two-sided 95% CI will be computed based on the Greenwood's formula.

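### Stratum A OS12 runs from diagnosis in patients who enter only after radiation, and the plan does not align its 40% null, or the 50% alternative, to patients alive at entry

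*Combined protocol and SAP*

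**What the plan says.** Section 9.3.1.4 sets the clock: "Overall survival (OS) is defined as the duration of time of diagnosis to time of death". Section 3.2.1 sets the entry condition: "Patients must have undergone radiation therapy and surgery as part of their standard of care". Table 6.1, footnote 15 (Strata A and B), adds that "Post radiation therapy MRI must occur within 14 days of enrollment". Section 10.3.2 sets the efficacy population: "Any subject enrolled (ITT) will be considered evaluable for clinical efficacy".

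Section 10.2.1 tests a null of 40% in 19 patients with a one-sided exact binomial test. It rejects at 12 or more alive at 12 months, with a stated 80% power at 70% and an actual alpha of 3.5%. Patients lost before 12 months count as events. The 40% equals the result of the cooperative-group radiation and temozolomide study, which resulted "in an OS12 rate of 40" per cent. The section also gives a 50% rate from PNOC003 and PNOC007 combined (unpublished). On comparability it says "For PNOC003 patients were enrolled prior to the start of radiation therapy - similar to the COG study", and that "none of the enrolled patients came off study due to progression during or at completion of radiation therapy making this a reasonable control group". It prints cutoffs of 10/19 and 14/19 for nulls of 30% and 50%, and leaves the null to be settled at analysis from recent publications and PNOC data.

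**The concern.** No analysed patient can die between diagnosis and entry, yet that interval counts towards the 12 months. A cohort enrolled before radiation can lose patients in the same interval. If it did, and its clock also started at diagnosis, its 12-month rate is too low a bar for patients already known to have survived to entry.

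The plan offers no landmark, no delayed-entry estimate, no early-death rate and no null conditional on entry. Its one comparability remark concerns PNOC003, which contributes to the 50% figure and not to the 40%.

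The 50% figure has a separate defect. PNOC007 is this trial: Section 1.3 reports its 19 DIPG patients and Section 10.2.2 its accrual. A null that includes the trial's own patients is pulled towards the result being tested, and Section 10.2.1 would allow PNOC data to set the null at analysis.

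OS12 is the primary efficacy endpoint of Stratum A and there is no concurrent control, so the efficacy inference rests on the null.

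**Working it through.** **The plan's own figures.** Exact binomial, n = 19:
- P(X ≥ 12 | 0.40) = 3.52% (stated 3.5%), and P(X ≥ 12 | 0.70) = 81.8% (stated 80%).
- P(X ≥ 10 | 0.30) = 3.3% and P(X ≥ 14 | 0.50) = 3.2%, so the alternative cutoffs are also right.

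The arithmetic of the design is sound. The question is which null applies.

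**Null for patients alive at entry.** Let b be the reference OS12 from diagnosis and e the share of the reference cohort dead before the entry point. Among patients alive at entry, OS12 = b / (1 − e). For example, 0.40 / 0.90 = 44.4%. Then alpha = P(X ≥ 12 | 19, b / (1 − e)).

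Three inputs are assumptions, because the documents do not give them:
- e is taken as 2% to 20%.
- The reference clock is taken to start at diagnosis. If it started later, the formula does not apply.
- A 35% base stands for a poorer expected outcome under H3.3K27M selection, which Section 1.1 links to shorter survival in DIPG.

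Alpha of 12/19 with no losses to follow-up:

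| Early deaths e | Null, 40% base | Alpha | Null, 35% base | Alpha |
|---|---|---|---|---|
| 0% | 40.0% | 3.5% | 35.0% | 1.1% |
| 2% | 40.8% | 4.1% | 35.7% | 1.4% |
| 5% | 42.1% | 5.3% | 36.8% | 1.8% |
| 10% | 44.4% | 8.0% | 38.9% | 2.8% |
| 15% | 47.1% | 12.0% | 41.2% | 4.4% |
| 20% | 50.0% | 18.0% | 43.8% | 7.1% |

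Alpha reaches 5% at a null of 41.81%. That corresponds to e = 1 − 0.40/0.4181 = 4.3% on the 40% base and e = 1 − 0.35/0.4181 = 16.3% on the 35% base.

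**Losses counted as deaths.** If a share l of would-be 12-month survivors is lost, the null for the observed count is b(1 − l) / (1 − e). On the 40% base:
- l = 5%: alpha is 3.5%, 5.4%, 8.3% and 12.8% at e = 5%, 10%, 15% and 20%.
- l = 10%: alpha is 2.3%, 3.5%, 5.5% and 8.7%.

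The two effects cancel when l = e. The loss rule is not a correction, however. It does nothing when follow-up is complete, and at a true 70% it cuts the power of 12/19 to 71.5% (l = 5%) or 59.6% (l = 10%).

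**Stricter cutoffs, 40% base, no losses.** At e = 5%, 10%, 15% and 20%:
- 13/19 has alpha 1.9%, 3.1%, 5.05% and 8.4%.
- 14/19 has alpha 0.5%, 1.0%, 1.7% and 3.2%.

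Power at a true 70% is 66.6% for 13/19 and 47.4% for 14/19.

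**The case against.** The plan sees part of the problem. Section 10.2.1 raises the timing of enrolment and reports no withdrawals for progression during or at completion of radiation in PNOC003. Under Section 7.2 of this protocol, "Subjects who expire without confirmation of disease status will be considered progressive disease at the time of death". If PNOC003 used the same rule, its record would imply few deaths through radiation. The printed 14/19 rule also holds alpha at 3.2% at the top of the assumed range.

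This has weight and narrows the point. But the remark concerns another cohort, the documents do not show that PNOC003 used that rule, and the weeks from the end of radiation to entry are not covered. Nothing requires 14/19, and the 50% null behind it includes this trial's own patients.

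Two stronger readings are tempting. A reader might infer that the 12/19 rule is anti-conservative. The documents do not support that: they give neither the early-death rate nor the time origin of the reference cohort, and H3.3K27M selection and the loss rule oppose the effect. On the 35% base alpha stays below 5% through 15% early deaths. A reader might also infer that this defect alone makes a result of 12/19 uninterpretable. Limited ability to separate treatment from selection belongs to any single-arm comparison with a historical rate, and aligning the null would reduce that difficulty, not remove it.

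**Conclusion.** The gap is real and can be read from the text: the clock starts at diagnosis, entry follows radiation, all enrolled patients are analysed, and neither the 40% nor the 50% null is shown to fit patients alive at entry. The lack of independence of the 50% figure is also plain from the text.

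The effect on alpha is not established. It could be negligible or material, depending on early deaths, losses, the prognosis of H3.3K27M-positive patients and the reference clock, and the net direction should not be asserted. On the 40% base with no losses the margin is thin: about 4% early deaths uses it up. This should be fixed in the analysis text and the report. It is not an error in the sample-size calculation.

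**What to change.** In Section 10.2.1:

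1. Exclude PNOC007 patients from any null used to test this trial.
2. Compare OS12 with an external rate that has the same time origin and is conditional on survival to post-radiation entry. State the resulting cutoff and its alpha.
3. Use one correction only. Either test the binomial count against that conditional rate, or use a delayed-entry Kaplan-Meier estimate against a benchmark conditional on survival to the earliest entry time. With 19 patients the delayed-entry estimate is unstable early, when few are at risk.
4. If no matched external rate exists, which is quite possible for H3.3K27M-positive patients, keep 12/19 as the stated rule. Report its alpha over the assumed range for both bases, show 14/19 (alpha 3.2% at a 50% null) as a sensitivity analysis, report the number lost before 12 months, and limit the efficacy conclusion accordingly.
5. State when the null was chosen. Section 5.1.5 reports all 19 Stratum A patients treated by the end of 2018, and PNOC007 outcomes already feed the 50% figure, so the choice cannot be called prospective.
6. Apply the same alignment to the Stratum C OS12 comparison.

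The cost is wording and analysis time. The diagnosis date is already collected at registration (Section 4.2), and no patients or procedures are added. If a stricter cutoff follows, power at 70% falls from 81.8% to 66.6% (13/19) or 47.4% (14/19). On the 40% base, 13/19 would still not hold 5% at 15% early deaths (5.05%).
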